7. DATA ANALYSIS

a. Sample size. For estimating the number of PCCs that will compose the sample in Catalonia, we have

considered that the mean migration rate in all settings is higher than 10%, then the achieved confidence level will exceed 95% when 32 centres or more are participating. A comparative analysis of the PCCs in relation to the migration density will be first performed to select the pairs of PCCs with more similar characteristics to assure the validity of the results.

- **b.** Feasibility and acceptability analysis. IDIs and FGs will be conducted in the PCCs, the latter with 8 to approximately an estimated maximum of 10 participants in each group. Data will be collected through digital audio recording. All IDIs and FGs will be manually transcribed by one interviewer and field notes will be made during or after the IDI/FG discussion. A thematic content analysis will be performed to evaluate the data from each IDI/FG. It will consist of six phases: become familiar with the data, generate initial codes, search for themes, review themes, define final themes and write-up. In order to validate the data, the coding and final categories will be triangulated by the research team. To complement this analysis, the analysis of the survey of the programme acceptance will be carried out.
- **c. Analysis impact of the tool**. The effectiveness of the tool will be evaluated and compared in each pair of PCCs, the intervention compared with the control group.
- **d.** The **primary outcome** measure will be the increased detection rate of all aggregated conditions included in the study in the intervention-PCCs compared with the control-PCCs. Conditions: Chagas diseases, strongyloidiasis, schistosomiasis, HIV, viral hepatitis B, viral hepatitis C, active tuberculosis and female genital mutilation.

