- 7. Infección tuberculosa latente (ITL): Se decidió que no se implementará el cribado de ITL en Cataluña ya que nunca se ha realizado un cribado de forma sistemática para la ITL en Atención Primaria (AP), además de que la mayoría de los centros de AP no tienen acceso a la prueba diagnóstica IGRA, la prueba más coste-efectiva para detectar la ITL. Aunque no se creará una alerta específica para la ITL durante el proyecto, se recomienda que en un futuro se promueva la formación para poder implementar está infección en programas de cribado llevados a cabo en AP.
- **8. Estrongiloidiasis:** Se recomienda el cribado serológico de estrongiloidiasis a la población inmigrante procedente de países endémicos y si alguno de estos individuos está inmunosuprimido o tiene un potencial riesgo de ser inmunosuprimido en un futuro, se debería derivar a la unidad especializada del hospital de referencia y se debería realizar estudio de parásitos en heces.
- **9. Esquistosomiasis:** Se recomienda el cribado serológico de esquistosomiasis a la población inmigrante procedente de países endémicos.
- **10.** Enfermedad de Chagas: Se recomienda el cribado serológico de *T. cruzi* a la población inmigrante procedente de países endémicos.
- 11. Mutilación genital femenina (MGF): Se recomienda valorar el riesgo de MGF y detectar los casos en niñas y mujeres procedentes de países endémicos. Además, es necesario formar a los profesionales de la salud en competencia intercultural y en cómo abordar la temática en la consulta respetando la cultura de la mujer y de su familia.
- **12. Derivación:** Personas diagnosticadas de alguna de las patologías incluidas en el programa de cribado deben ser derivadas a la unidad especializada del hospital de referencia.

Annex 2. Screening recommendations for infectious diseases and FGM targeting the migrant population residing in Andalusia, Spain.

- 1. Población diana: Se ha definido como población diana del estudio a inmigrantes que procedan de países en África, Latino América, Asia y Europa del Este. Se utilizó la división geográfica de la Comisión de Estadística de las Naciones Unidas.
- 2. Virus de la inmunodeficiencia humana (VIH): Se recomienda el cribado universal de VIH a todos los inmigrantes procedentes de un país incluido en la definición de población diana si no se ha hecho una prueba de VIH con anterioridad. Repetir prueba de VIH si la persona es diagnosticada con otra ITS y/o presenta otros factores de riesgo.

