- **3. Otras infecciones de transmisión sexual (ITS):** Se recomienda el cribado universal de sífilis a todos los inmigrantes procedentes de un país incluido en la definición de población diana si no se ha hecho una prueba de sífilis con anterioridad. Repetir prueba de sífilis si la persona es diagnosticada con otra ITS y/o presenta otros factores de riesgo.
- **4. Virus de la hepatitis B (VHB)**: Se recomienda realizar el cribado de VHB mediante la detección del antígeno australiano (HBsAg) y el anticuerpo contra el antígeno core (anti-HBc) a todos los inmigrantes procedentes de un área con prevalencia intermedia o alta de VHB (≥2%). *Además, se ofrecerá cribado de VHB a inmigrantes procedentes de Marruecos y Guinea Ecuatorial, aunque la prevalencia en estos países es <2%.

Se ofrecerá pauta vacunal a las personas con un test serológico negativo.

- **5. Virus de la hepatitis C (VHC):** En el contexto del plan para la eliminación de la hepatitis C en Andalucía, se recomienda el cribado universal de VHC a todos los inmigrantes procedentes de un país incluido en la definición de población diana.
- **6. Tuberculosis (TB) activa:** Se recomienda el cribado de TB por Mantoux a inmigrantes asintomáticos recién llegados (<5 años) procedentes de países con una incidencia >50 casos/100.000 habitantes. Si el resultado es positivo o dudoso, realizar radiografía de tórax.
- 7. Infección tuberculosa latente (ITL): De acuerdo con el protocolo de actuación que se va a implementar en el Distrito Sanitario de Atención Primaria Poniente, se recomienda lo siguiente, a inmigrantes <35 años, procedentes de países con una incidencia >50 casos/100.000 habitantes, que se puedan tratar y que no tengan contraindicaciones para el tratamiento de la infección tuberculosa latente:
- i) Tratar si procede a las personas con resultados de Mantoux >20mm.
- ii) Realizar IGRA y tratar si procede a personas vacunadas con resultados de Mantoux de 5-19mm para inmigrantes del Magreb y África subsahariana y de 10-19mm para el resto de los inmigrantes incluidos en la población diana.
- *Además, se incluirán en la recomendación la población inmigrante procedente de Marruecos, aunque la incidencia en este país es <50 casos/100.000 habitantes y se considerará realizar IGRA y tratar si procede a personas vacunadas con resultados de Mantoux de 5-19mm.
- **8. Estrongiloidiasis:** Se recomienda el cribado serológico de estrongiloidiasis a la población inmigrante procedente de países endémicos.

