2.2 Specific Study Objectives

Primary objective 1: To compare the detection rate per month of all aggregated infections (HIV, HBV, HCV, TB, *T.cruzi*, *S.stercoralis* and *Schistosma spp.* infections) between the intervention and control centres over at least five years until the end of the intervention. In the Andalusian site, syphilis, latent TB and intestinal parasites will also be included.

Secondary objective 2: To compare the detection rate per month of each individual condition, the infections and FGM cases, between the intervention and control centres over at least five years until the end of the intervention.

Secondary objective 3: To compare the number of early HIV diagnoses between the intervention and control centres over at least five years until the end of the intervention.

Secondary objective 4: To compare the number of early HBV and HCV diagnoses between the intervention and control centres over at least five years until the end of the intervention.

Secondary objective 5: To compare the number of screening tests performed for all aggregated infections between the intervention and control centres over at least five years until the end of the intervention.

Secondary objective 6: To compare the number of screening tests performed for each individual condition between the intervention and control centres over at least five years until the end of the intervention.

Secondary objective 7: To estimate associations between the screening performance of all aggregated infections with different socio-demographic and epidemiological factors.

Secondary objective 8: To estimate associations between the screening performance of each individual condition with different socio-demographic and epidemiological factors.

Secondary objective 9: To measure the number of the diagnosed individuals with follow-up visits in the hospital of reference.

Secondary objective 10: To measure the number of the diagnosed individuals that have received treatment.

Secondary objective 11: To estimate the prevalence of each infection and FGM in the migrant population.

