2.3 Endpoints

Primary Endpoints

Endpoint 1: For the detection rate of all aggregated infections, the monthly detection rate based on positive serologies, chest radiographies, the International Classification of Diseases Ninth Revision (ICD-9 for Andalusia) or Tenth Revision (ICD-10 for Catalonia) of FGM and/or gynaecologist referrals will be considered within the migrant patients who visited their assigned centre during the intervention period. Also, positive tuberculin skin test (TST) and/or Interferon Gamma Release Assay (IGRA) and stool samples will be considered for the Andalusian site. Control and intervention PCCs will be compared before and after the implementation.

Secondary Endpoints

Endpoint 2: For the detection rate of each individual condition, the infections and FGM, the monthly detection rate based on positive serologies, chest radiographies, ICD-9/ICD-10 of FGM and/or gynaecologist referrals, TST/IGRA and stool samples (for Andalusia) will be considered within the migrant patients who visited their assigned centre during the intervention period. Control and intervention PCCs will be compared before and after the implementation.

Endpoint 3: The number of early diagnoses of HIV will be assessed using the CD4 cell count of migrant patients diagnosed with an HIV infection, and will be compared between the control

and intervention PCCs before and after the implementation. If possible, we will estimate the monthly detection rate of early HIV diagnoses and also compare it between the intervention and control PCCs.

Endpoint 4: The number of early diagnoses of HBV and HCV will be assessed using the levels of transaminases, platelets, bilirubin, and clotting parameters from blood analyses of migrant patients diagnosed with HBV or HCV, and will be compared between the control and intervention PCCs before and after the implementation. If possible, we will estimate the monthly detection rate of individuals diagnosed with HBV or HCV presenting high levels of transaminases, platelets, bilirubin, and clotting parameters and also compare it between the intervention and control PCCs.

Endpoint 5: The number of the screening tests performed of all aggregated infections (serological tests, chest radiographies, TST or IGRA tests and stool samples in the case of the Andalusian site) will be compared between the intervention and control PCCs before and after the implementation.

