| | FGM (completed | |
| | questionnaires) | |
| Associations with the scre | ening performance for all | Bivariate and multivariate |
| aggregated infections | | analysis |
| | HIV | |
| | Syphilis^ | |
| Associations with the | HBV | Bivariate and multivariate |
| screening performance | HCV | analysis |
| for each individual | active TB | |
| condition | latent TB^ | |
| | T.cruzi infections | |
| | S.stercoralis infections | |
| | Schistosoma spp. infections | |
| | Intestinal parasites^ | |
| | FGM | |
| Patients under follow-up a | after diagnosis | Bivariate analysis |
| Patients under treatment | after diagnosis | Bivariate analysis |
| Cured patients | | Bivariate analysis |
| | HIV | |
| | Syphilis^ | |
| | HBV | Numerator: number of |
| Prevalence of each | HCV | detected cases for each |
| condition | active TB | specific condition. |
| | latent TB^ | Denominator : number of |
| | T.cruzi infections | tested patients for each |
| | S.stercoralis infections | specific condition. |
| | Schistosoma spp. infections | |
| | Intestinal parasites^ | |
| | FGM | |

HIV: human immunodeficiency virus, HBV: hepatitis B virus, HCV: hepatitis C virus, TB: tuberculosis, FGM: female genital mutilation, TST: tuberculin skin test, IGRA: Interferon Gamma Release Assay; ^Only in the Andalusian site; The detection rate of all aggregated infections and the individual conditions will be calculated using the numbers of diagnoses per month over at least five years until the end of the intervention.

Figure 1. Flow chart of the migrant population

Figure 2. Monthly detection rates of the aggregated infections

Figure 3-9. Monthly detections of each individual condition (infections and FGM)

8. Reporting Conventions

Dates will be reported using the format MM/DD/YYYY. P-values will be reported to 3 decimal places. P-values less than 0.001 will be reported as '<0.001'. Statistics such as means, standard deviations, median values and percentages, will be calculated using the same decimal digits as the raw data. Rounding off will be performed on the final calculation value and reported according to publication requirements.

9. Technical Details

The data of the ISMiHealth study will be analysed with Stata Statistical Software: Release 16. At the time of the writing, the operating system of the computer that will be used for the analysis is Windows.

10. Summary of Changes to the Protocol

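### The SAP's Andalusian primary aggregate contains three infections that the protocol's primary outcome lacks, and no rule stops it counting one infection twice

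*SAP*

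**What the plan says.** Protocol section 7.d gives one primary outcome for a trial in both regions: "Conditions: Chagas diseases, strongyloidiasis, schistosomiasis, HIV, viral hepatitis B, viral hepatitis C, active tuberculosis and female genital mutilation".

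SAP section 2.2, primary objective 1, lists seven infections without FGM and then extends the list: "In the Andalusian site, syphilis, latent TB and intestinal parasites will also be included". SAP section 2.3, Endpoint 1, makes this operational: "Also, positive tuberculin skin test (TST) and/or Interferon Gamma Release Assay (IGRA) and stool samples will be considered for the Andalusian site". The same endpoint also counts positive serologies, chest radiographies and FGM codes or gynaecology referrals. The footnote to SAP Table 4 says that detection rates "will be calculated using the numbers of diagnoses per month over at least five years until the end of the intervention".

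Protocol Annex 2 (Andalusia) describes TB screening in two steps. Item 6 starts with Mantoux: "Se recomienda el cribado de TB por Mantoux a inmigrantes asintomáticos recién llegados (<5 años". It continues: "Si el resultado es positivo o dudoso, realizar radiografía de tórax". Item 7 treats latent TB separately and limits it to people under 35 from countries above an incidence threshold, with Morocco added.

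SAP section 6, under the Andalusian analysis, says that an analysis of syphilis, latent TB and intestinal parasites will be done in addition. SAP section 10 cites protocol version 1.0 and reports no substantive change to methods. The protocol under review, version 8.0, still lists the eight conditions.

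**The concern.** A primary outcome should be the same set of events in the protocol and the SAP. Here an analyst of the Andalusian data could defend at least three aggregates: the protocol's eight conditions, the SAP's seven infections, or the SAP's seven plus three. The choice could be made after the data are seen, and it can change the answer.

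The second issue is the numerator. It is a number of diagnoses, with separate SAP Annex 1 variables for active and latent TB and for *S. stercoralis*, *Schistosoma* and intestinal parasites. There is no rule of one case per person or per organism. SAP Annex 1 has separate screening-criteria variables for each of these conditions. If the tool leads to more paired testing, double entries could become more frequent in intervention centres after implementation, and the difference in differences would not remove them.

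**Working it through.** **1. The aggregates side by side**

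| Source | Components in Andalusia | FGM |
|---|---|---|
| Protocol 7.d | 8 conditions (7 infections + FGM) | in |
| SAP 2.2, objective 1 | 7 + 3 = 10 infections | not listed |
| SAP 2.3, Endpoint 1 | the above tests, plus FGM codes or referrals | in |
| SAP 6, Andalusia | the three additions analysed in addition; in or out of the aggregate unclear | not addressed |

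No two of the first three rows agree.

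**2. Where one infection can be entered twice**

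- *TB.* Under Annex 2 item 6 a positive or doubtful Mantoux leads to a radiograph. SAP Table 4 assigns TST/IGRA to latent TB and radiography to active TB, and Endpoint 1 counts a positive result on either. A Mantoux-positive person with active TB meets both criteria. Item 6 sets no upper age limit and item 7 does, so a positive Mantoux outside the latent TB criteria could also enter. Protocol section 6 names radiography alone for active TB. I follow Annex 2 as the Andalusian text; the two passages need reconciling.
- *Helminths.* Annex 2 item 10 recommends stool testing for parasites without listing organisms. *S. stercoralis* and *Schistosoma* are counted by serology under their own headings, and nothing excludes them from the stool category.

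**3. Share of the additions**

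The documents state no yields, and the SAP gives no sample-size figure for Andalusia to reproduce. Let A be the yield of the three additions, B that of the seven shared infections, and r = A/B. The share is A/(A+B) = r/(1+r): r = 0.5 gives 33%, r = 1 gives 50%, r = 3 gives 75%. The additions exceed half only if A > B.

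Assumed ranges per 100 attending migrants: B = 1, 3, 6 or 10; latent TB eligible 10–50% and positive 5–30%; syphilis 0.5–4%; stool testing eligible 2–30% and positive 5–30%.

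- Lowest: A = 100 × (0.10×0.05 + 0.005 + 0.02×0.05) = 1.1; share = 1.1/(1.1+10) = 10%.
- Highest: A = 100 × (0.50×0.30 + 0.04 + 0.30×0.30) = 28; share = 28/(28+1) = 97%.
- Over the 972 combinations the median is 67%, and 74% of them exceed one half; at B = 10 only 37% do. These proportions describe the grid and are not probabilities.

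**4. Why the choice matters**

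Suppose the tool doubles detection of the additions and does nothing for the shared infections. The composite rate ratio is (1 + 2r)/(1 + r): 1.20 at r = 0.25, 1.50 at r = 1 and 1.75 at r = 3. On the shared infections alone it is 1.00.

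**5. Size of the double counting**

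Let f be the part of B that is strongyloidiasis, schistosomiasis or active TB, and d the fraction of those also counted under stool or TST/IGRA. Extra cases relative to B are f × d. For assumed f = 0.1–0.5 and d = 0–1 this runs from 0 to 0.5 × 1 = 50%.

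**The case against.** The additions have a basis: Annex 2 recommends screening for all three in Andalusia, and SAP section 6 says the regional algorithms differ. Every condition also has its own detection rate (SAP objective 2, Table 4), so the shared infections remain visible. Both points stand. They justify reporting the additions, but not placing them in a primary aggregate that the protocol does not define.

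Separate fields for active and latent TB may mean that clinicians record only one, and Annex 2 item 7 asks for IGRA in some vaccinated people, so a positive Mantoux is not automatically a latent TB diagnosis. That stands too: double counting is possible under Endpoint 1 as written, not established.

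Several stronger readings are tempting and are not supported:

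- *The additions would dominate the result.* With equal numbers tested for every condition, and assumed positivity of 25.8% summed over the seven, 2% for syphilis, 10–35% for latent TB and 5–15% for parasites, the additions make up 0.17/0.428 = 40% to 0.52/0.778 = 67%. But Annex 2 contradicts equal testing: HIV and HCV screening is universal, while latent TB and stool testing are restricted. Even on those inputs, Mantoux plus stool fall below half in three of six combinations (0.15/0.428 once, 0.25/0.528 twice).
- *The protocol itself ties stool study to strongyloidiasis.* The words "se debería realizar estudio de parásitos en heces" are in the Catalan annex and concern immunosuppressed people. The gap lies in Annex 2 and the SAP.
- *The district latent TB roll-out confounds the result.* Annex 2 item 7 says "De acuerdo con el protocolo de actuación que se va a implementar en el Distrito Sanitario de Atención Primaria Poniente". A roll-out even across arms would largely cancel in a difference in differences, and no uneven one is documented.
- *The mismatch spoils the comparison with Catalonia.* SAP sections 5.1 and 6 plan separate analyses. Screening criteria for HIV, HCV, Chagas disease and TB differ between the annexes in any case.

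**Conclusion.** Two things hold on the text alone. The SAP's Andalusian primary aggregate contains three infections that the protocol's primary outcome lacks, with SAP section 6 unclear on whether they belong in it. As written, the aggregate can count one TB or helminth infection under two headings. A reader might infer that the additions would drive the result, or that infections are in fact counted twice; the documents establish neither. The ranges of 10–97% for the share and 0–50% for the extra cases rest wholly on the assumptions stated above.

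The consequence is limited. Catalonia is analysed separately and is unaffected. On the SAP's figures Andalusia is a preliminary comparison of three against three centres. If these are three randomised pairs, the smallest two-sided randomisation p-value is 2/2³ = 0.25, so no confirmatory claim is at risk. The point should be corrected because it concerns the primary outcome and costs little.

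**What to change.** 1. Define one primary aggregate, word for word the same in protocol 7.d, SAP objective 1 and SAP Endpoint 1, and use it in both regions. State whether FGM is in it; a seven-infection list alone would still differ from the protocol.
2. Report syphilis, latent TB and intestinal parasites as Andalusian secondary rates, or as a named extended aggregate. Objective 2 already covers the individual rates, so no information is lost.
3. Add a counting rule: each person counts at most once per pathogen. An active TB case is not also counted as latent TB. *Strongyloides* or *Schistosoma* found in stool counts only under its own heading.
4. List the organisms that make up intestinal parasites, and state which test results define a latent TB case in the numerator.
5. Reconcile SAP section 6 (Andalusia) with objective 1.

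The cost is SAP wording, alignment of the protocol's list if FGM is dropped, one de-duplication step in the data preparation, and a smaller Andalusian primary count. A common list makes the two regional results more consistent, but not fully comparable, because eligibility differs by region.

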2.3 Endpoints

Primary Endpoints

Endpoint 1: For the detection rate of all aggregated infections, the monthly detection rate based on positive serologies, chest radiographies, the International Classification of Diseases Ninth Revision (ICD-9 for Andalusia) or Tenth Revision (ICD-10 for Catalonia) of FGM and/or gynaecologist referrals will be considered within the migrant patients who visited their assigned centre during the intervention period. Also, positive tuberculin skin test (TST) and/or Interferon Gamma Release Assay (IGRA) and stool samples will be considered for the Andalusian site. Control and intervention PCCs will be compared before and after the implementation.

Secondary Endpoints

Endpoint 2: For the detection rate of each individual condition, the infections and FGM, the monthly detection rate based on positive serologies, chest radiographies, ICD-9/ICD-10 of FGM and/or gynaecologist referrals, TST/IGRA and stool samples (for Andalusia) will be considered within the migrant patients who visited their assigned centre during the intervention period. Control and intervention PCCs will be compared before and after the implementation.

Endpoint 3: The number of early diagnoses of HIV will be assessed using the CD4 cell count of migrant patients diagnosed with an HIV infection, and will be compared between the control

and intervention PCCs before and after the implementation. If possible, we will estimate the monthly detection rate of early HIV diagnoses and also compare it between the intervention and control PCCs.

Endpoint 4: The number of early diagnoses of HBV and HCV will be assessed using the levels of transaminases, platelets, bilirubin, and clotting parameters from blood analyses of migrant patients diagnosed with HBV or HCV, and will be compared between the control and intervention PCCs before and after the implementation. If possible, we will estimate the monthly detection rate of individuals diagnosed with HBV or HCV presenting high levels of transaminases, platelets, bilirubin, and clotting parameters and also compare it between the intervention and control PCCs.

Endpoint 5: The number of the screening tests performed of all aggregated infections (serological tests, chest radiographies, TST or IGRA tests and stool samples in the case of the Andalusian site) will be compared between the intervention and control PCCs before and after the implementation.

Endpoint 6: The number of the screening tests performed for each individual condition will be compared between the intervention and control PCCs before and after the implementation.

Endpoint 7: Associations between the screening performance of the aggregated infections with different socio-demographic and epidemiological factors, such as, sex, age, geographic areas immunosuppression status, being attended in an intervention centre, fulfilling the screening criteria, among others, will be analysed.

Endpoint 8: Associations between the screening performance of each individual condition with different socio-demographic and epidemiological factors, such as, sex, age, geographic areas immunosuppression status, being attended in an intervention centre, fulfilling the screening criteria, among others, will be analysed.

Exploratory Endpoints

Endpoint 9: The number of migrant patients under follow-up in the hospital after a diagnosis of an infection or FGM will be estimated using the Minimum basic dataset (MBDS).

Endpoint 10: The number of migrant patients under treatment after a diagnosis will be estimated using the data from the EPR systems and MBDS.

Endpoint 11: The prevalence of each condition will be estimated using as the denominator the total number of tested migrant patients for that specific condition.

3. Study Methods

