|---------------------------------|---------------------------------|----------------|----------|-----------------|----------|
| Centre | | | | | |
| Type of centre (urban or rural) | | | | | |
| Index of socioeconomic | | | | | |
| deprivation (MEDEA index) | | | | | |
| Arm of the intervention | | | | | |
| Patient | | | | | |
| Sex | | | | | |
| Age | | | | | |
| Area of birth^ | | | | | |
| Assigned PCT | | | | | |

| Referrals to specialists | | | |
|-----------------------------------|--|---|--|
| Drugs prescribed during the | | | |
| intervention | | | |
| Other diagnoses | | | |
| Immunosuppression status | | | |
| Migrants with screening criteria | | | |
| for XX^ | | | |
| CD4 cell count, viral load and/or | | | |
| laboratory parameters* | | | |
| Hospitalisation | | | |
| Follow-up visits after | | | |
| hospitalisation | | | |
| Mortality | | _ | |

PCT: primary care team, XX: aggregated infections or any of the conditions, OR: odds ratio, aOR: adjusted odds ratio, CI: confidence interval; Region will be used as a random intercept for the logistic regressions; ^Only one of these variables will be added to the multiple logistic regression model due to highly correlation; *When applicable

Table 4. Description of the methodology employed for each outcome

| Outcome | | Methodology |
|--|---------------------------------|------------------------------------|
| Detection rate of all aggre | gated infections | Difference in differences analysis |
| | HIV cases | |
| | Syphilis cases^ | |
| | HBV cases | |
| Detection rate of each | HCV cases | Difference in differences |
| individual condition | active TB cases | analysis |
| | latent TB cases^ | |
| | T.cruzi infection cases | |
| | S.stercoralis infection cases | |
| | Schistosoma spp. infection | |
| | cases | |
| | Intestinal parasites cases^ | |
| | FGM cases | |
| Early diagnoses of | HIV | Bivariate analysis and, if |
| infections | HBV | possible, difference in |
| | HCV | differences analysis |
| Screening tests performed of all aggregated infections | | Bivariate analysis |
| | HIV | |
| | Syphilis^ | |
| | HBV | |
| Screening tests | HCV | |
| performed for each | active TB (chest radiographies) | Bivariate analysis |
| individual condition | latent TB^ (TST/IGRA) | |
| | T.cruzi infections | |
| | S.stercoralis infections | |
| | Schistosoma spp. infections | |

| | Intestinal parasites^ | |
|----------------------------|-----------------------------|--------------------------------|

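### Early HIV, HBV and HCV diagnosis is undefined in the SAP, and the optional HBV/HCV rate counts people with high markers rather than early cases

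*SAP*

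**What the plan says.** SAP section 2.2 sets two objectives on early diagnosis: "To compare the number of early HIV diagnoses between the intervention and control centres" (objective 3) and "To compare the number of early HBV and HCV diagnoses between the intervention and control centres" (objective 4).

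SAP section 2.3 turns these into Endpoints 3 and 4.

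- **HIV, main measure:** "The number of early diagnoses of HIV will be assessed using the CD4 cell count of migrant patients diagnosed with an HIV infection". No CD4 value that separates early from late is given.
- **HIV, optional measure:** where possible, a monthly detection rate of early HIV diagnoses.
- **HBV/HCV, main measure:** "The number of early diagnoses of HBV and HCV will be assessed using the levels of transaminases, platelets, bilirubin, and clotting parameters". No direction, cut-off or timing relative to diagnosis is given.
- **HBV/HCV, optional measure:** where possible, a monthly detection rate of "individuals diagnosed with HBV or HCV presenting high levels of transaminases, platelets, bilirubin, and clotting parameters".

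SAP Table 4 assigns early diagnoses a bivariate analysis and, where possible, difference in differences, with no denominator. Its footnote says that detection rates for the aggregated infections and individual conditions "will be calculated using the numbers of diagnoses per month over at least five years until the end of the intervention". Table 2 summarises CD4 count and laboratory parameters by mean or median only. Annex 1 lists these markers as plain quantitative variables. SAP section 6 does not describe the early-diagnosis analysis, and the secondary outcomes in protocol section 7 do not include it.

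**The concern.** Protocol section 1 justifies screening partly by the complications that early identification can prevent. Endpoints 3 and 4 are the endpoints that address stage at diagnosis, so they need to separate finding more cases from finding cases earlier.

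Three features stand in the way.

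- **No definition.** Early is not defined for any of the three infections. Extraction is retrospective, so the definition could be chosen after the data are in hand.
- **A mismatched optional rate.** The one HBV/HCV case description in the SAP concerns people with high markers, under an objective about early diagnosis.
- **Counts without a share.** A number of early diagnoses rises whenever more people are diagnosed, even if the mix of stages does not change.

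A tool that finds more cases at the same stage could be reported as bringing diagnosis forward. The optional HBV/HCV rate could rise or fall for reasons that its label does not reveal.

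**Working it through.** The SAP gives no figure for Endpoints 3 and 4, so there is nothing to reproduce. Its sample-size statement (section 4) concerns the primary outcome. All counts and shares below are assumptions.

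**1. The text, side by side.** For HIV, the optional rate repeats the target of the objective (early diagnoses). For HBV/HCV, the sentence in the same position drops the word early and describes high markers. Raised transaminases, bilirubin and clotting times point towards liver damage, and platelets fall as liver disease advances; both are general clinical knowledge, not statements in the documents. So if the rate is meant to be early, high is the wrong direction for transaminases, bilirubin and clotting. If it is meant to be late, high is wrong for platelets. No reading makes the sentence right for all four. It also does not say whether a person needs one high marker or all of them.

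**2. Counts follow total detection.** Early count = diagnoses × early share.

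- Assume 60 v 30 diagnoses (intervention v control) and 70% early in both arms.
- Early counts: 60 × 0.70 = 42 v 30 × 0.70 = 21.
- Count ratio: 42/21 = 2, equal to the detection ratio 60/30 = 2.
- Difference in early share: 0.70 − 0.70 = 0.

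With equal baselines in the two arms, a difference in differences reduces to this same contrast.

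How often would such a count difference be significant? Take 60% early in both arms, detection ratio R and e early cases in the control arm. Use a two-sided 0.05 Wald test on the log ratio of Poisson counts, ignoring clustering: z = ln R / √(1/e + 1/(R·e)).

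- 100 control diagnoses, so e = 60, at R = 1.5: z = 0.405/√(1/60 + 1/90) = 0.405/0.167 = 2.43, and the chance of significance is 0.68.
- Same e at R = 1.25 and R = 2: 0.25 and 0.99.
- R = 1.5 with 50 and 200 control diagnoses: 0.41 and 0.93.

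These are not false positives for early yield, which really does differ. They are the chance of a significant result that could be misread as earlier diagnosis.

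**3. The optional HBV/HCV rate.** High-marker count = diagnoses × high share. For simplicity, take the high share as 1 − early share.

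- Same mix, 30% high in both arms: 60 × 0.30 = 18 v 30 × 0.30 = 9. The rate doubles with no stage shift.
- Intervention arm improves to 15% high: 60 × 0.15 = 9 v 9. The rate shows no difference, while early cases are 60 × 0.85 = 51 v 30 × 0.70 = 21.

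In general the high-marker ratio falls below 1 once the intervention arm's high share drops below (control high share)/R. With 40% high in controls, that threshold is 0.40/1.25 = 0.32, 0.40/1.5 = 0.27, 0.40/2 = 0.20 and 0.40/3 = 0.13.

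With 100 control diagnoses (40 high, 60 not high) and R = 1.5:

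| High share, intervention | High-marker count v 40 | Ratio | Not high v 60 |
|---|---|---|---|
| 40% (unchanged) | 60 | 1.50 | 90 |
| 30% | 45 | 1.125 | 105 |
| 20% | 30 | 0.75 | 120 |

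At fixed R, the more the mix improves, the lower the rate. Its sign alone does not tell whether diagnosis became earlier.

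**The case against.** A reader might infer that Endpoint 4 as a whole is reversed and counts damaged livers as early cases. The documents do not support that. The high-marker wording belongs only to the optional sentence. The main HBV/HCV count names the markers without a direction, so it is undefined, and a sensible definition would make it work.

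The optional sentence may also be an unlabelled comparator for advanced disease, since it never calls these people early. That is possible, but the SAP does not say so, and the platelet wording is wrong on that reading too.

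A reader might also infer that comparing counts is an error. It is not. The objectives ask for numbers, and a screening tool that doubles detection at an unchanged mix does find twice as many early cases. A share among the diagnosed has its own weakness: it conditions on being diagnosed, which happens after randomisation and which the tool itself changes.

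The 9 v 9 result needs the optional rate to be read alone, and the high share to halve exactly as diagnoses double. Read beside a well-defined main count of 51 v 21, it would not mislead. Bivariate analysis in Table 4 could include a share, but no share is specified.

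**Conclusion.** The point holds in a limited form. The optional HBV/HCV rate does not match its objective, and its direction for platelets conflicts with the other markers. The main HIV, HBV and HCV counts lack the definitions needed to compute them reproducibly. The counts are valid as early yield, but with an unchanged stage mix they rise in exact proportion to total detection, so alone they cannot support a claim of earlier diagnosis.

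The sizes shown rest on assumed numbers of diagnoses and stage shares, and the test probabilities ignore clustering. The proportionality and the sign-change threshold are arithmetic and do not depend on those values. The direction of the liver markers is general clinical knowledge. The primary endpoint is unaffected; this should be corrected but does not threaten the main comparison.

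**What to change.** 1. Reword the optional rate in Endpoint 4. Either count early HBV/HCV diagnoses, parallel to the HIV sentence, or label it a rate of late or advanced diagnosis. State the direction for each marker, with platelets low as the sign of damage, and say whether one or all markers are required.
2. Have the sponsor's clinicians set the cut-offs, including CD4, and the sampling window around diagnosis, before data extraction.
3. Keep the early counts or rates. Beside them report, by arm and period, the early share among new HIV, HBV and HCV diagnoses. Note that this share is imprecise for rare conditions and conditions on being diagnosed.

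Cost: mostly SAP wording, plus some additions to Annex 1. The markers are listed there, but the primary-care laboratory values have no sample date, diagnoses are yes/no without a date, and clotting is one unspecified coagulation field. Sample dates, diagnosis dates and the named clotting parameter should be added. Diagnosis dates, or an equivalent, are needed for the monthly detection rates in any case.
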